#### *2. Current amount cigarette smoked/day*

Current amount of cigarette smoked/day will be included as a continuous variable. Also a categorical variable of the originally reported average daily consumption will be created as follows: no smoking, 10 cigarettes per day (CPD) or less; 11-20 CPD; more than 20 CPD.

### *3. Current Snus use*

Participants will be grouped as current snus users if they reported daily or occasional snus use. A categorical variable for current snus use will be created (non-current snus user= 1, current daily or occasional snus user= 2)

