### ***Exposure Variables***

Tobacco use (cigarette smoking and/or snus use) will be considered as exposure as follows:

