#### *1. Current Cigarette Smoking*

Participants will be grouped as current cigarette smokers if they reported daily or occasional smoking. A categorical variable for current smoking status will be created (non-current smoker = 1, current daily or occasional smokers=2)

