## **Covariates**

We will include sex, age, cohabitation, education, employment, co-morbidity due to a tobacco-related disease and country of residence as covariates in the study. The covariates will be defined as follows:

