### **Statistical analysis**

Risk ratios (RR) and their corresponding 95% CI for COVID-19 infection, hospitalization, ICU, or death due to COVID-19 will be estimated through generalized linear models (GLM). We will use the Poisson family with robust standard errors and the maximum likelihood optimization algorithm to estimate the relative risk of a confirmed COVID-19 case, hospital admission, ICU, or death due to COVID-19 (Zou, 2004). First, adjusted Poisson regression (Zou, 2004) will be applied to assess the influence of exposure (smoking or snus) on the study's outcomes. If we assume that  $y_{ij}$  is the observed binary outcome (COVID-19 infection, hospital admission, ICU, or death due to COVID-19) for subject  $i$  in country  $j$ , the specification and the equation of the Poisson model is as follows:

$$\log(p_{ij}) = \beta_0 + \beta_1 X_{1ij} + \sum_k^R \beta_k X_{ijk} \quad (1)$$

where  $p_{ij}$  is the probability of the outcome  $y_{ij}$ ,  $X_{1ij}$  is the exposure (smoking/snus),  $\beta_0$  is the intercept,  $\beta_1$  is the regression coefficient corresponding to the exposure,  $X_{ijk}$  represents the subject's values of  $R$  covariates, and  $\beta_k$  is a regression coefficient corresponding to each covariate. Exponentiating  $\beta_1$  gives the corresponding relative risk, RR.

We will then apply a multilevel regression (Goldstein, 1995) which assumes that each country has its own COVID-19 infection probability, and this varies from one country to another. This will be the primary analytical model. In this multilevel model, the Poisson regression for COVID-19 infection will include an additional term  $u_j$ , which is the country-level random effects as a predictor variable:

$$\log(p_{ij}) = \beta_0 + \beta_1 X_{1ij} + \sum_k^R \beta_k X_{ijk} + u_j \quad (2)$$

In this model, the probability depends on the value of the random effects  $u_j$  which is the totality of unmeasured country-level variables that predict COVID-19 infection and are uncorrelated with the individual variables in the model.

As a secondary analysis, we will use a negative binomial count model (Hilbe, 2011, 2014) to assess inpatient length of stay (i.e. the cumulative number of days of hospitalization) as a measure of disease severity among tobacco users compared to non-tobacco users.

We will carry out stratified analyses by sex, age, education, and time period.

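### The smoking and snus models neither adjust for nor restrict on the other tobacco product, so the snus estimate cannot bear on the nicotine question raised in the Background

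*Combined protocol and SAP*

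**What the plan says.** The plan is a combined protocol and SAP. Its Background states that widespread snus use in these countries will make it possible to separate out a role for nicotine.

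- **Exposure Variables.** The opening line reads "Tobacco use (cigarette smoking and/or snus use) will be considered as exposure as follows". Three variables follow: current smoking ("non-current smoker = 1, current daily or occasional smokers=2"), cigarettes per day, and current snus use ("A categorical variable for current snus use will be created (non-current snus user= 1, current daily or occasional snus user= 2"). None is conditional on the other product, and none is a joint or exclusive-use category.
- **Covariates.** "We will include sex, age, cohabitation, education, employment, co-morbidity due to a tobacco-related disease and country of residence as covariates in the study". Neither product is on the list.
- **Statistical analysis, models (1) and (2).** Adjusted Poisson regression is used "to assess the influence of exposure (smoking or snus"). There is one exposure term with one coefficient, and its variable "is the exposure (smoking/snus").
- **Statistical analysis, length of stay.** The negative binomial model treats length of stay "as a measure of disease severity among tobacco users compared to non-tobacco users". No variable is derived for that contrast.
- **Stratified analyses.** "We will carry out stratified analyses by sex, age, education, and time period".
- **Sensitivity analyses.** There are three: adding comorbidity and employment; prospectively collected data only, in Cox models specified like the primary analysis; and competing risks for death. None adjusts for, or restricts on, the other product.

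**The concern.** To learn about nicotine from snus, one must compare snus users with people who use neither product, or otherwise hold smoking fixed. The written models do not. A person counted as not using snus may smoke, and a dual user is exposed in both the smoking and the snus model.

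An apparent snus association, or the absence of one, could therefore be a smoking effect. The direction depends on the overlap between products, which the documents do not give. If snus mostly replaces smoking the bias goes one way, and if it accompanies smoking it goes the other way. A large pooled sample does not shrink this bias; it only narrows the interval around the biased value. Leaving the contrast open also allows it to be chosen after results are seen, on a question that the Background itself calls controversial.

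**Working it through.** The plan gives no figure on this point to reproduce. The check is textual (above), followed by an illustration of size.

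**1. Inputs.** From the Background: smoking RR for infection 0.67 (0.60-0.75). This is used for illustration only, because the Background warns that most such studies may be biased. Assumed, not in the documents:
- overall smoking P = 11%
- overall snus use S = 10%
- smoking among snus users ps = 5%, 20% or 30%
- smoking RR for severe outcomes 1.5-2.0
- true snus RR = 1

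**2. Formula.** Smoking among non-users of snus is pn = (P - S·ps)/(1 - S). With smoking RR r, the apparent snus RR is (1 + ps(r - 1)) / (1 + pn(r - 1)).

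**3. Smoking among non-users of snus.**
- ps = 5%: (0.11 - 0.005)/0.90 = 11.67%
- ps = 20%: (0.11 - 0.02)/0.90 = 10.00%
- ps = 30%: (0.11 - 0.03)/0.90 = 8.89%

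**4. Apparent snus RR when snus has no effect.**

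| ps | r = 0.60 | r = 0.67 | r = 0.75 | r = 1.5 | r = 2.0 |
|---|---|---|---|---|---|
| 5% | 1.028 | 1.023 | 1.017 | 0.969 | 0.940 |
| 20% | 0.958 | 0.966 | 0.974 | 1.048 | 1.091 |
| 30% | 0.912 | 0.928 | 0.946 | 1.101 | 1.194 |

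Example: ps = 30% and r = 0.67 give (1 - 0.30 × 0.33)/(1 - 0.0889 × 0.33) = 0.901/0.971 = 0.928. At ps = 11%, pn is also 11% and the ratio is 1.000 for every r.

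**5. The smoking estimate.** If snus has no effect, all smokers carry risk r and all non-smokers carry risk 1, whether or not they use snus. The smoking model then returns r exactly.

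**6. Would it be enough to put both products in as main effects?** Suppose either product, alone or together, has RR 0.67 against neither, with P = 11% and S = 10%. With smoking as the only exposure and ps = 20%, the non-smokers (89%) are 8% snus only and 81% neither. Their mean relative risk is (0.08 × 0.67 + 0.81)/0.89 = 0.970, and the smoking RR is 0.67/0.970 = 0.690. Poisson fits to the expected cell counts give:

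| ps | Smoking RR, smoking alone | Smoking RR, both main effects | Snus RR, snus alone | Snus RR, both main effects |
|---|---|---|---|---|
| 5% | 0.694 | 0.681 | 0.697 | 0.682 |
| 20% | 0.690 | 0.710 | 0.693 | 0.714 |
| 30% | 0.688 | 0.726 | 0.690 | 0.734 |

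In this scenario, main effects come closer to 0.67 at 5% overlap but lie further away than the written models at 20% and 30%. A four-level exposure returns 0.67 by construction, because it is saturated in the two products. That is not evidence for it; its merit is that it makes no no-interaction assumption.

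**7. Cell sizes.** In the Swedish cohort of 424,386, with 10% snus use and 5-30% overlap:
- dual users: 424,386 × 0.10 × 0.05 = 2,122 to 424,386 × 0.10 × 0.30 = 12,732
- snus only: 424,386 × 0.10 × 0.70 = 29,707 to 424,386 × 0.10 × 0.95 = 40,317

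At an assumed ICU or death risk of 0.05-0.10%, that is about 1-13 dual-use events and 15-40 snus-only events.

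**The case against.** **The plan does treat the products separately.** It defines separate variables and runs smoking or snus as the exposure. This stands. A reader might infer that the products are merged throughout or never distinguished, and the text does not support that. What is missing is separation of their independent effects.

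**Joint modelling is not excluded.** This also stands. The opening line on exposure allows combined use, and nothing forbids a joint model. But the plan names its confounders one by one, adds two more in a sensitivity analysis, and lists smoking in neither place. It therefore cannot be read as having specified the adjustment.

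**Nicotine is rationale, not the aim.** The aim paragraph speaks of tobacco use, infection and adverse outcomes, without nicotine. That limits the weight of the point. The Background nevertheless makes a firm claim about what the snus data will show, and the written analysis cannot deliver it.

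**The size rests on assumptions.** True. Prevalences, overlap and severe-outcome RRs are assumed, both ranges include 1, and the infection bias is modest. The figures are crude. The models adjust for sex and age, so the bias after adjustment could be smaller or larger.

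**A four-level variable does not isolate nicotine.** True as far as it goes. Only current use is classified, so former smokers fall in both snus only and neither. If snus replaces smoking, past smoking confounds that contrast. The fix has to say so.

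**Conclusion.** The point holds. As written, the snus estimate mixes snus with smoking and cannot inform the nicotine question. Under the assumptions stated, a null snus effect could appear as an RR of 0.91-1.03 for infection or 0.94-1.19 for severe outcomes. It would be 1.00 if snus users and non-users smoked equally often. The textual omission is certain; the size and direction of the bias cannot be settled from the documents.

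A reader might infer that the smoking results are unsound as well. The documents do not support that: the smoking estimate is distorted only if snus itself affects the outcome, and in the illustration it is unbiased. Nor do they support a claim that the snus bias runs in a known direction.

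**What to change.** In the Statistical analysis section, covering the main models and the sensitivity analyses:

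1. Among participants with both products recorded, fit a four-level current exposure (neither, smoking only, snus only, both; reference neither) in models (1) and (2), the length-of-stay model and the Cox models. Name snus only versus neither as the contrast for the nicotine question. The reference group also gives the length-of-stay comparison a defined meaning.
2. Where the dual-use cell is too small (ICU, death), leave dual users out and compare each exclusive-use group with neither. Do not fall back on a main-effects model that assumes no interaction.
3. Keep the smoking-alone model, so that people without snus data are not lost.
4. State that current-use categories do not remove confounding by past smoking. Repeat the snus-only contrast in Sweden, adjusted for or restricted on past smoking; Data Sources says past use is recorded there.

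The cost is SAP wording and one variable derived from two exposures already harmonised, plus Swedish past use for item 4. There are three downsides. Dual-use cells will be sparse for ICU and death. Norwegians without January 2021 snus data drop out of the four-level analysis. Norwegian snus use was recorded after follow-up ended in December 2020. No separate check without Norway is needed for that last point, because the planned sensitivity analysis of Sweden and the 2018-2019 Finnish surveys already excludes it.

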## **Outcome Variables**

The study will include five outcomes: any diagnosis of COVID-19, hospital admission for COVID-19, length of hospital stay for COVID-19; intensive care use due to COVID-19, and death attributable to COVID-19. The follow-up period for all outcomes was from February 2020 until December 2020.

### *1. Any diagnosis of COVID-19:*

Sweden: at least a positive polymerase chain reaction test (PCR) reported by the laboratories to Sweden's national electronic surveillance system for communicable diseases, SmiNet

Finland: cases with a positive SARS-CoV-2 RT-PCR, either informed by a laboratory or by a physician as a record of an ICD-10 code U07.1 (which requires a positive SARS-CoV-2 RT-PCR).

Norway: a positive test for SARS-CoV-2 based on PCR obtained from The Norwegian Surveillance System for Communicable Diseases (MSIS) or the presence of antibodies for SARS-CoV-2.

Out of these definitions a categorical variable will be created (No recorded COVID-19 diagnosis= 1, registered COVID-19 diagnosis= 2)

## *2. Hospital admission for COVID-19*

Any hospital admission with a diagnosis of COVID-19 (ICD-10 codes U071 and U072). The diagnosis could be registered either as a main or as a concomitant diagnosis.

- A. A categorical variable for hospital admission with any diagnosis of COVID-19 (either main or secondary diagnosis) will be created (No admissions= 1, any admission= 2).
- B. A categorical variable for hospital admission with COVID-19 as the main diagnosis only (No admissions= 1, any admission= 2).

## *3. Intensive unit care because of a diagnosis of COVID-19*

Admission to an intensive care unit (ICU) because of a diagnosis of COVID-19 (ICD-10 codes as above). A categorical variable for intensive unit care because of a diagnosis of COVID-19 (No/Yes) will be created (No ICU care= 1, any ICU care= 2).

## *4. Death for COVID-19*

Death due to COVID-19 will be established using the Swedish, Finnish, and Norwegian Cause of Death Registries. All deaths occurring during the follow-up period with COVID-19 registered as the main cause will be included. The restriction to main cause will be done to maximize the specificity of the diagnosis (Ioannidis, 2021). A categorical variable for death due to COVID-19 will be created (Alive at the end of follow-up= 1, Death during follow-up= 2).

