We will carry out three sensitivity analyses. First, we will analyse the data adding tobacco-related comorbidity and employment as additional confounders with data from Sweden and Norway. Second, we will analyse only data prospectively collected to explore the influence of information bias. For this purpose, we will include data from Sweden and Finnish data from 2018 and 2019. This data will be analyzed with Cox proportional hazards models with the same specifications as the primary analysis. We will use time in study as the timescale. Participants will be censored due to end of follow-up or the occurrence of the event.

Third, for death of COVID-19, we will also include a competing risk analysis to take right-censoring due to a death non-attributable to COVID-19 into account. Competing risk means that a subject can experience one of a set of different events during the study period. Accordingly, the use of traditional methods of survival analysis, such as the Kaplan-Meier survival function, will result in incidence estimates that are biased upward, irrespective of the independence between the competing events (Austin et al., 2016; Berry et al., 2010; Kim, 2007; Southern et al., 2006). Instead, we will use two models to fit a regression in the presence of competing risk, the cause-specific hazard modeling and the sub-distribution hazard modeling (Austin et al., 2016). The cause-specific hazard function implies the instant rate of occurrence of a specific event in subjects who have not experienced yet any of the different types of events (Andersen et al., 2002; Austin et al., 2016). If we consider two types of events, death due to COVID-19 causes and death due to non-COVID-19 causes, then the cause-specific hazard of COVID-19 death implies the instant rate of COVID-19 death in subjects who have not yet experienced

either event (Austin et al., 2016). In the cause-specific hazards regression model, we will model the effect of covariates by using the traditional Cox proportional hazards model after censoring individuals with competing events at the time of their occurrence.

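### COVID-19 death is defined by main cause only; if main-cause coding differs by tobacco use the death RR may be biased, and no second definition checks this

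*Combined protocol and SAP*

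**What the plan says.** Under Outcome Variables, 4. Death for COVID-19, there is one rule: "All deaths occurring during the follow-up period with COVID-19 registered as the main cause will be included". The stated reason is specificity: "The restriction to main cause will be done to maximize the specificity of the diagnosis". The resulting variable has two levels, "Alive at the end of follow-up= 1, Death during follow-up= 2", with no level for a death in which COVID-19 contributed but was not the main cause.

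The section on hospital admission faces the same choice and handles it differently. It notes that "The diagnosis could be registered either as a main or as a concomitant diagnosis" and defines two variables. One is broad: "A categorical variable for hospital admission with any diagnosis of COVID-19 (either main or secondary diagnosis) will be created". The other is narrow: "A categorical variable for hospital admission with COVID-19 as the main diagnosis only".

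Under Statistical analysis, death is analysed like the other binary outcomes: "Risk ratios (RR) and their corresponding 95% CI for COVID-19 infection, hospitalization, ICU, or death due to COVID-19 will be estimated". The one sensitivity analysis specific to death is a competing-risk analysis with two event types, "death due to COVID-19 causes and death due to non-COVID-19 causes". A separate sensitivity analysis adds tobacco-related comorbidity and employment to the model, using Swedish and Norwegian data only.

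**The concern.** Specificity is half of what an RR needs from an outcome definition. The other half is that the definition finds true cases equally well in both exposure groups. Here there is a concrete route by which it might not. Tobacco can cause chronic disease, and such a disease can be entered as the main cause when an infected person dies. COVID-19 is then at most a contributing cause, and the death is not counted.

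If this happens more often in smokers than in non-smokers, smokers lose more of their COVID-19 deaths from the count and the RR moves down. A harmful association would look weaker, or a null one protective. The Background warns against misleading protective findings and says that tobacco's role in death is unclear. The biases it names are selection and confounding; differential coding of the outcome would be a further route to the same misreading.

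**Working it through.** The documents give no expected death RR, event count or coding data, so there is no figure of the plan's to reproduce. All capture shares below are assumptions.

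**1. Basic relation.** Let Se1 and Se0 be the shares of true COVID-19 deaths coded as main cause in users and non-users. With specificity close to 1:

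observed RR = true RR × Se1 / Se0

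| Se1 | Se0 | Factor | True 1.10 becomes | True 1.20 becomes |
|---|---|---|---|---|
| 0.95 | 0.95 | 1.00 | 1.10 | 1.20 |
| 0.90 | 0.95 | 0.947 | 1.04 | 1.14 |
| 0.85 | 0.95 | 0.895 | 0.98 | 1.07 |

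The sign is not fixed. With Se1 = 0.90 and Se0 = 0.85 the factor is 0.90 / 0.85 = 1.06, which is upward.

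**2. The comorbidity route.** Suppose capture depends only on whether the person who died had a tobacco-related disease. If c is the share with such disease among COVID-19 deaths in a group:

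Se = c × (capture with disease) + (1 − c) × (capture without disease)

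Assume c = 0.30 in non-users, and capture of 0.95 without disease.

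- Mild case: c = 0.40 in users, capture 0.90 with disease. Se1 = 0.40 × 0.90 + 0.60 × 0.95 = 0.930; Se0 = 0.30 × 0.90 + 0.70 × 0.95 = 0.935; factor 0.995.
- Strong case: c = 0.70 in users, capture 0.60 with disease. Se1 = 0.70 × 0.60 + 0.30 × 0.95 = 0.705; Se0 = 0.30 × 0.60 + 0.70 × 0.95 = 0.845; factor 0.834.
- Equal c in both groups: factor 1.0.
- Within a comorbidity stratum: factor 1.0, because by assumption capture then no longer depends on exposure.

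**3. Do the planned analyses show it?**

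- *Poisson models.* I read a death with another main cause as a non-event; the two-level coding does not say where such deaths fall.
- *Cause-specific hazard model.* A COVID-19 death coded to lung or heart disease is a competing event and is censored.
- *Sub-distribution hazard model.* The same death stays in the risk set without ever becoming an event.
- *Comorbidity-adjusted analysis.* By step 2 it could remove part of the bias if coding depends on comorbidity. However, the variable is binary, Finland is left out, and employment enters at the same time. Tobacco-related disease may also lie on the causal path. A change in the RR could not be attributed to coding.

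**4. What a broader definition would do.** Count COVID-19 as main or contributing cause, and assume this finds every true case. Let f be the number of incidental deaths per true COVID-19 death in non-users, and r the RR for incidental deaths:

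RR(any mention) = (true RR + f × r) / (1 + f)

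For f from 0 to 0.20 and r of 1 or 2:

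- A true RR of 1.0 becomes 1.00 to 1.17 (upper end: (1.0 + 0.20 × 2) / 1.20).
- A true RR of 1.3 becomes 1.25 to 1.42 (lower end: (1.3 + 0.20 × 1) / 1.20; upper end: (1.3 + 0.20 × 2) / 1.20).

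The broader definition therefore has its own error, upward when r exceeds the true RR. It is a check, not a replacement.

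**The case against.** A reader might infer that the death RR is biased downward as a matter of fact, and for tobacco as a whole. The documents do not support that, for four reasons.

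- They hold no data on cause-of-death coding by tobacco use, and the sign depends on Se1 / Se0.
- The reference groups are non-current smokers and non-current snus users, so former users sit among the unexposed. They may carry tobacco-related disease, including any who quit because of illness. This narrows the assumed gap in comorbidity and could close or reverse it.
- Smoking and snus are separate exposures. The comorbidity argument is made for smoking and does not carry over to snus without further reasons.
- The comorbidity-adjusted analysis could remove part of any such bias.

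The plan's choice is also reasoned. False positives distort an RR, and step 4 shows that an any-mention count can be wrong too. Two definitions for admission do not make one definition for death an error.

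All of this stands against asserting a bias or replacing the main-cause definition. It does not answer the narrower point: the specificity argument rests on similar capture in both groups, and no planned analysis tests that condition.

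**Conclusion.** The point holds as a conditional one. The death RR may be biased, plausibly downward for smoking, if COVID-19 deaths in users are less often coded with COVID-19 as main cause than those in non-users. Size and sign cannot be learned from the documents. With assumed capture of 85% to 90% against 95%, the factor is 0.89 to 0.95. Under the wider comorbidity assumptions it runs from 0.834 to 0.995. At equal capture it is 1.0 and the plan's reasoning is sound.

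The competing-risk models cannot reveal the problem, and the comorbidity-adjusted analysis can neither fully address nor isolate it. One of the five outcomes is affected. This is an inexpensive improvement worth making; the main-cause definition is not a mistake.

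**What to change.** - In section 4, Death for COVID-19, keep main cause as definition A. Add, as a sensitivity analysis, definition B: COVID-19 as main or contributing cause. This mirrors the two admission variables, although there the letters run the other way (A is the broad one).
- Apply B where the cause-of-death registries supply contributing causes. The plan names the three registries but does not say that contributing causes are available, so confirm this by country.
- Run the Poisson models and both competing-risk models on A and on B, separately for smoking and for snus. Report both sets and interpret any divergence.
- State in advance that A may err low if coding differs by tobacco use, and that B may err high through incidental COVID-19 deaths. Conclusions need not depend on A and B agreeing: agreement would have to be defined, and both could err in the same direction.
- State where deaths from other causes fall in the two-level death variable.

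The cost is one more registry variable and repeat model runs. The downside is that B admits some incidental deaths, which is why it stands beside A and does not replace it.
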